6.1 Primary Analysis

This analysis will be done for NVAF patients presenting with first ischemic acute stroke and treated with dabigatran within 3 months of index event.

To describe the distribution of dabigatran treatment initiation times in patients with non-valvular atrial fibrillation (NVAF) after hospitalization for first-ever ischemic stroke (the index event) treated with dabigatran, we will

1. Create a histogram of initiation times by day.
2. Calculate mean, standard deviation and 95% (Standard Normal) confidence intervals (CI) of the Mean, as well as the median, interquartile ranges, minimum and maximum values.
3. Create frequency table by time periods. Give the absolute count of subjects and the proportion of subjects in each group. The time periods to be considered are 0-24h, >24-72h, >3-7d >7-14d, >14-28d, >28d-3m, however these categories may be revised depending on the distribution of initiation times to ensure sufficient patient numbers in each category.

We do not expect to have any missing values in the time to dabigatran treatment initiation. However, if there are missing values collected, they will be summarized in the frequency table as a separate category. Proportions for all other categories will not include the missing values in the denominator (as this is what has been done in previous works for all previous SITS-MOST and/or SITS-ISTR publications [P07-00880, P08-11746].). The proportion of missing values will be out of all subjects sampled.

6.2 Secondary Analysis:

These analyses will be done for NVAF patients presenting with first ischemic acute stroke and treated with dabigatran within 3 months of index event.

6.2.1 To describe baseline characteristics for patients treated with dabigatran according to time of dabigatran initiation.

Descriptions will only be done for the subgroups (of time to initiation) consisting of at least 100 patients. We Will:

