Provide the mean, SD and 95% (Student's T based or Resampling method based) CI for all continuous or the proportion and Clopper-Pearson 95% CI for all binary or categorical (within each category) for all subject baseline characteristics for all time periods, with time periods defined as in the primary analysis section. We will use the standardized difference < 10% in absolute value as indicating a negligible difference in the mean or prevalence of a covariate between groups. The earlier initiation time category will be used as the reference group for calculation of the standardized differences. No P-values will be provided for these comparisons.

1. run univariate and multivariable regression models with the dependent variable time-to-initiation as a continuous variable in days, the independent variables in these models will include age and baseline stroke severity as measured by NIHSS score at index stroke, pre-stroke functional status by mRS, prior treatment with anticoagulation, Signs of current/ acute infarction in the brain imaging scans, CHA2DS2-VASc stroke risk score as the continuous value and/or categorized into low, intermediate and high risk and HAS-BLED bleeding risk score by the mean and/or categorized into low or high risk. We will run a linear (or log-linear) regression model. Complete case analysis will be performed (exclusion from the regression of subjects with at least one missing value on any of the predictors or outcome analyzed). P-values

will not be adjusted for multiple comparisons. Other baseline variables, for example those identified in analysis 1, may be included in one or more of the models. However, P-values and confidence intervals will not be reported from these investigations.

2. Make scatter or boxplots of each of time-to-initiation by each baseline characteristics of interest

6.2.2 To describe self-reported factors important for the physician's decision as to the time of dabigatran initiation in the post-ischemic stroke setting.

For Question 1 ("Reasons to delay start of oral anticoagulation therapy"), we will, for NVAF patients presenting with first ischemic acute stroke and treated with dabigatran within 3 months of index event:

1. Make frequency tables of physician responses

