2. Make frequency tables of reasons by time period for each physician response with time periods as defined in the primary analysis. Time periods with less than 100 patients will not be considered. Comparisons of the distribution of reasons between different time periods may be made and a standardized difference of 10% or more in absolute value will be considered notable.
3. Make frequency tables of time periods by physician responses (reasons) with time periods as defined in the primary analysis. Reasons with less than 100 patients will not be considered. Comparisons of the distribution of time periods between different reasons may be made and a standardized difference of 10% or more in absolute value will be considered notable.

For Question 2 ("Reasons for not planned to start oral anticoagulation therapy"), a descriptive analysis (frequency tables of physician responses) will be done for NVAF patients presenting with first ischemic acute stroke and not receiving any OAC within 3 months of index event.

6.2.3 To describe self-reported factors important for the physician's decision as to the dose of dabigatran in the post-ischemic stroke setting.

For NVAF patients presenting with first ischemic acute stroke and treated with dabigatran within 3 months of index event, we will:

1. Make frequency tables for physician responses to question "Reasons for the dose of oral anticoagulation"
2. Make frequency tables for physician responses (reasons) for each dose categories 110, or 150 mg 2 times daily. Comparisons of the distribution of reasons between the dose categories may be made and a standardized difference of 10% or more in absolute value will be considered notable. Subgroup analysis for dose will only be performed if there are at least 100 patients in the subgroup
3. Make frequency tables for dose category (110, or 150 mg 2 times daily) for each physician response (reason) with at least 100 patients. Comparisons of the distribution

of dose between the reasons provided may be made and a standardized difference of 10% or more in absolute value will be considered notable.

:

7 Appendixes

7.1 Appendix 1

SITS Variables names particularly important for this study

Patient/ file code
Country name
Hospital/ Centre code
Gender
Age At Stroke Onset
Participation In Other Trials
Treatment at baseline
Aspirin
Dipyridamole
Clopidogrel
Other Antiplatelet
Anticoagulants- Yes/ No/ Unknown

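### The 10% standardized-difference labels in SAP 6.2.1 to 6.2.3 rest on a point estimate in groups as small as 100, with no confidence interval planned for that difference (minor)

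*SAP*

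**What the plan says.** SAP 6.2.1 (secondary objective B) compares baseline characteristics between time-to-initiation periods. It will "use the standardized difference < 10% in absolute value as indicating a negligible difference in the mean or prevalence of a covariate" between groups, with the earlier period as reference. This rule is planned, not optional. The entry condition is "Descriptions will only be done for the subgroups (of time to initiation) consisting of at least 100 patients". Each period's own mean gets a 95% CI, and for other variables the SAP gives "the proportion and Clopper-Pearson 95% CI for all binary or categorical" variables. It adds "No P-values will be provided for these comparisons". It also plans to "run univariate and multivariable regression models with the dependent variable time-to-initiation as a continuous variable in days", for a named list of predictors.

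SAP 6.2.2 items 2 and 3 (objective C) and 6.2.3 items 2 and 3 (objective D) plan frequency tables of the physicians' reasons. Comparisons are permitted rather than required; 6.2.2 item 2, for example, says "Comparisons of the distribution of reasons between different time periods may be made". Where they are made, "a standardized difference of 10% or more in absolute value will be considered notable". The floor is again 100 patients per period, dose group or reason. No interval of any kind is stated in these two sections.

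The six time periods are not fixed: SAP 6.1 item 3 says "these categories may be revised depending on the distribution of initiation times to ensure sufficient patient numbers in each category". Both reason questions in SAP 3.3 (C, Question 1, and D) allow several answers per patient. Protocol 9.5 expects about 1000 dabigatran patients. The 95% CIs listed in Protocol 9.7 are for baseline and demographic descriptives, so they do not supply an interval for the standardized difference.

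**The concern.** Each rule turns an estimate into a word without regard to its precision. The two rules fail in opposite directions, so their error rates must be kept apart:

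- **6.2.1** attaches a word only below 10%. The risk is that a real difference between early and late starters is reported as negligible.
- **6.2.2 and 6.2.3** attach a word only at 10% or above. The risk is that a reason is reported as notable when its true frequency does not differ between the groups.

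Comparisons between reasons raise a further question. In 6.2.2 item 3 and 6.2.3 item 3 the groups are patients for whom a given reason was ticked. One patient can be in several groups, and the SAP does not say how this is handled.

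At stake is the reading of objective B, and of C and D if the comparisons are made. Protocol 9.9 sees exploratory results as a source of hypotheses for later studies, and a label often set by sampling variation screens for these poorly.

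**Working it through.** **Inputs.** Cut-off 0.10 (SAP 6.2.1 to 6.2.3); floor of 100 per group (same sections); about 1000 patients (Protocol 9.5); six periods (SAP 6.1). The SAP gives no formula for the standardized difference; I take the difference divided by the root of the average of the two variances. The documents state no power or precision for these comparisons, so there is no figure to reproduce. Splits other than the floor are my assumptions: 167 vs 167 is 1000/6 per period, 100 vs 900 is the most uneven two-group split the floor allows, and 500 vs 500 is the most even.

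**Formula for disjoint groups.** SE(d) = sqrt(1/n1 + 1/n2 + d²/(2(n1 + n2))), with the estimate taken as normal.

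**Worked case, 100 vs 100.**
- At d = 0, SE = sqrt(0.02) = 0.141. The cut-off is 0.10/0.141 = 0.71 SE, so P(at or beyond 10%) = 2 × (1 − Φ(0.707)) = 0.480.
- At d = 0.20, SE = sqrt(0.02 + 0.04/400) = 0.142. P(below 10%) = Φ(−0.705) − Φ(−2.116) = 0.240 − 0.017 = 0.223.
- At d = 0.30, P(below 10%) = 0.077.
- The 95% half-width is 1.96 × 0.141 = 0.277. An observed 5% (labelled negligible in 6.2.1) has a CI of −23% to +33%. An observed 10% (labelled notable in 6.2.2 and 6.2.3) has a CI of −18% to +38%.

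| Split | SE at d = 0 | 6.2.1: true 20% read as negligible | 6.2.2/6.2.3: true 0 called notable | 95% half-width |
|---|---|---|---|---|
| 100 vs 100 | 0.141 | 22% | 48% | 27.7 points |
| 167 vs 167 | 0.109 | 18% | 36% | 21.4 points |
| 100 vs 900 | 0.105 | 17% | 34% | 20.7 points |
| 500 vs 500 | 0.063 | 6% | 11% | 12.4 points |

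**Simulation check at 100 vs 100 (200,000 runs).** For a continuous variable, chance crossing is 48.1%, and a true 20% falls below 10% in 22.2% of runs. For a binary variable, chance crossing is 48.4%, 49.0% and 52.5% at prevalences of 10%, 30% and 50%.

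**Precision ceiling for disjoint groups.** A half-width of 10 points needs 2 × (1.96/0.10)² = 768.3, so 769 per group, or 1538 in two groups. About 1000 patients cannot supply that.

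**Overlapping reason groups, equal size.** Let two reasons have n patients each, k of them shared. The contrast is (1 − k/n) times the difference between the non-shared patients, and its SE at no difference is sqrt(2(n − k))/n. For n = 100:
- k = 50: SE 0.100; the non-shared patients must differ by 20% to read 10%; chance crossing is 32%.
- k = 75: SE 0.071; they must differ by 40%; chance crossing is 16%.

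In a simulation with a binary outcome and no true difference (4000 runs), a patient-level bootstrap 95% CI covered 95%, 94% and 95% at k = 0, 50 and 75. An independent-groups CI covered 94–95%, 99% and over 99.9%, so it is too wide under overlap.

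**Overlapping reason groups, unequal size.** Suppose reason A has 400 patients, reason B has 100, 50 are shared, and the shared patients sit 0.4 SD above everyone else. Mean A = 50 × 0.4/400 = 0.05 and mean B = 50 × 0.4/100 = 0.20. The contrast reads about 15%, although the non-shared patients do not differ.

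**The case against.** The case for leaving the SAP alone is substantial. The study is descriptive, with no power claim and no P-values for these comparisons, and SAP 5 calls all findings hypothesis generating. In 6.2.1 a reader has each period's estimate and CI, can approximate an interval for the difference, and has regressions for age, NIHSS, mRS, prior anticoagulation, infarct signs and both risk scores. In 6.2.2 item 2 and 6.2.3 item 2 the groups are disjoint, so an interval can be derived from the tables. The comparisons there are optional. Periods may be merged, so 100 vs 100 is the worst case.

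Most of this stands, and it limits the severity. It does not remove the point. The caveat in SAP 5 rests on selection into treatment, not on imprecision. The labelling rule in 6.2.1 does not use the CIs, the regressions name only some of the listed covariates, and merging is allowed rather than required.

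Three stronger readings are tempting and should not be drawn:

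- *Overlap always shrinks the contrast.* This holds for groups of equal size. With unequal groups it can go either way, as the 400 vs 100 example shows.
- *The study can never show that a difference lies within ±10%.* This holds for disjoint groups only. Two reasons with 500 patients each and 250 shared need 750 patients and give SE = sqrt(2 × 250)/500 = 0.045, a half-width of 8.8 points.
- *Nearly half of all labels are wrong.* The 48% applies only to the notable label, only at the floor, and only if the optional comparisons are made. It is not an error rate for 6.2.1.

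**Conclusion.** The concern holds as a minor reporting point. At the SAP's floor the 10% line is smaller than one standard error. The planned rule in 6.2.1 would then read a true 20% difference as negligible in 22% of cases, falling to 6% at 500 vs 500. A true 30% difference would be read so in at most 8%, so large differences are still found. If the comparisons in 6.2.2 and 6.2.3 are made, a true difference of zero would be called notable in 48% of cases at the floor, 34% to 36% at the intermediate splits and 11% at 500 vs 500. For disjoint groups from about 1000 patients the best half-width is 12.4 points, so a difference within ±10% cannot be shown there. Comparisons between reasons need a method that allows shared patients.

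These figures assume a normal estimate, independent patients and the splits shown; only the floor of 100 comes from the SAP. A reader might infer that the secondary objectives fail or that the two labels must be deleted. The documents do not support that: the tables and group summaries remain valid descriptions, and 10% can serve as a size marker. The primary analysis does not use the rule.

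**What to change.** In SAP 6.2.1, and in 6.2.2 and 6.2.3 wherever a comparison is made:

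- Report each standardized difference with its 95% CI.
- Use the words negligible and notable only beside that CI, and state that they describe the size of the estimate and are not a verdict.
- Add no significance rule, such as requiring the CI to exclude zero.

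For 6.2.2 item 3 and 6.2.3 item 3:

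- State that reason groups can share patients.
- Obtain the CI by a bootstrap that resamples patients, or compare patients with the reason cited against those without it. For dose, the second option uses the same 2×2 table as 6.2.3 item 2.

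**Cost.** Some SAP wording, extra table columns for every covariate and period comparison, a bootstrap program for the reason comparisons, and fewer categorical statements in the report. With up to six periods and long reason lists the added output is not trivial. No data, study-size or primary-analysis change is needed.

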9. RESEARCH METHODS**9.1 STUDY DESIGN**

This is an observational, multinational, multicentre, study in patients with NVAF presenting to a hospital with a first acute ischemic stroke. The study is based on existing data recorded in the SITS International Registry by physicians in European countries, such as Italy, United Kingdom, Czech Republic, Sweden, Germany, Poland, Spain, Finland, Portugal, Slovakia, Denmark, Estonia, Norway Belgium, Hungary, Slovenia, Croatia, Austria, Lithuania, France, Greece, Netherlands, Ireland, Ukraine and Iceland. All patients with NVAF will be included that present with the first ever ischemic stroke. For these patients baseline and demographics variables are available such as medical history including comorbidities and concomitant medications. Characteristics will further be used to estimate common stroke (CHADS₂, CHA₂DS₂-VAS_c) and bleeding (HAS-BLED) risk scores. Details on NVAF and secondary stroke prevention: time since first diagnosis, prior anticoagulation treatment, dose, and stroke severity of index event measured by National Institute of Health Stroke Scale (NIHSS) score, are recorded in the registry.

For patients that receive dabigatran within 3 months of the index event, details on post-stroke treatment (time from hospital admission – start and dose of dabigatran treatment for stroke prevention in NVAF, concomitant medication) will be analysed. Variables for physician's decision when to initiate oral anticoagulation with dabigatran post-ischemic stroke and the dose selected will be analysed.

In addition any start/stop of dabigatran treatment and doses prescribed will also be assessed at discharge and at 3 months after the index event.

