9.2 SETTING

Patients with NVAF presenting with their first ever acute ischemic stroke who are registered in the SITS International Registry from 1 July 2014 until approximately 31 July 2018 will be included in the study.

Inclusion criteria

- Patients with non-valvular Atrial Fibrillation (NVAF)
- Patients presenting with their first acute ischemic stroke
- ≥ 18 years of age

Exclusion criteria

- Documentation that the patient was enrolled or is planned to be enrolled in an investigational clinical trial at the time of the onset of the index event and for the duration of the data collection

Protocol for observational studies based on existing data

BI Study Number 1160-0235

c03412460-01

Proprietary confidential information © 2017 Boehringer Ingelheim International GmbH or one or more of its affiliated companies

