At baseline: Demographic data, NIHSS and pre-stroke mRS, blood pressure, laboratory values (plasma glucose, cholesterol, coagulation status, liver function, kidney function,) medical history including comorbidities and concomitant medication, results of imaging scans, CHADS₂, CHA₂DS₂-VASc and bleeding risk by HAS-BLED scores.

At 24 hours: NIHSS score, blood pressure, laboratory and imaging scans if performed.

During hospital stay: details of concomitant medications, additional imaging scans prior to start of dabigatran treatment, any start/stop/change dabigatran treatment any results of the imaging scans

At 7 day or discharge if occurred earlier than 7 days: Date/time discharge, NIHSS scores, blood pressure, type of stroke and AF, medications

SITS is an academic-driven, non-profit, international collaboration. It is an initiative by the medical profession aimed at driving excellence in acute and secondary stroke treatment, and to develop new knowledge and leading research.

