If yes, specify Anticoagulants- Not specified/ Warfarin/ Dabigatran/ Apixaban/ Rivaroxaban/ Edoxaban/ Other
If specify Anticoagulant chosen then, dose of Dabigatran as free text
Heparin/ Heparinoids for Stroke Prevention
Heparin/ Heparinoids for Prophylaxis Deep Venous Thrombosis
Anti-diabetic, oral
Insulin
Antihypertensive, IV
Antihypertensive, oral
Statin
Other treatment
NSAIDS
Risk factors at baseline
Hypertension
Diabetes
Hyperlipidaemia
Smoking
Previous Stroke
Previous TIA
Atrial fibrillation' (AF)

 • Valvular AF • Non-valvular AF

 • Not specified
Congestive Heart Failure
Systemic embolism
Vascular disease- with sub-classification
If Yes,

 • Myocardial infarction, • Complex aortic plaque • Peripheral arterial disease (PAD)
Abnormal kidney function (defined as the presence of chronic dialysis or renal transplantation or serum creatinine $\geq 200 \mu\text{mol/L}$).
Abnormal liver function (defined as chronic hepatic disease (e.g. cirrhosis) or biochemical evidence of significant hepatic derangement (e.g. bilirubin $> 2 \times$ upper limit of normal, in association with aspartate aminotransferase/alanine aminotransferase/alkaline phosphatase $> 3 \times$ upper limit normal)
Bleeding (history and/or predisposition to bleeding, e.g. bleeding diathesis, anaemia, etc. 'Labile INRs' refers to unstable/high INRs or poor time in therapeutic range (e.g. $< 60\%$).
Drugs/alcohol use (concomitant use of drugs, such as antiplatelet agents, non-steroidal anti-inflammatory drugs, or alcohol abuse, etc. If a patient is not on VKA/Warfarin the value for 'labile INRs' will not be assessed)
Modified Rankin Scale (mRS) Before Stroke
NIHSS score
Systolic Blood Pressure
Diastolic Blood Pressure
Plasma glucose
Cholesterol
Temperature
APTT
Weight
Length
Current Infarct CT/MR
ASPECTS Score CT/MR
Time logistics
Time For Pick up
Hospital Arrival Date
Date Time Of Alarm
Date Time Of imaging
Date Time Of Acute intervention
Type of Acute Intervention
Intravenous thrombolysis
Intraarterial thrombolysis

 • Dose Of Actilyse
Mechanical thrombectomy
During hospital stay
Rules: Questions below will be activated if;

 • Previous stroke or TIA = NO

• Non-valvular Atrial Fibrillation = YES
• Oral anticoagulation (OAC)
○  Yes  No  Unknown
○ If Yes,

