▪ Warfarin derivatives
▪ New OAC (NOAC)
• If NOAC
○ Dabigatran
○ Apixaban
○ Rivaroxaban
2h follow up
Systolic Blood Pressure
Diastolic Blood Pressure
NIHSS
24h follow up
NIHSS
Systolic Blood Pressure
Diastolic Blood Pressure
Current Infarct CT/MR
ASPECTS Score CT/MR
Local Haemorrhage CT/MR
Remote Haemorrhage CT/MR
Cerebral Oedema CT/MR
At discharge/ 7d
Diagnosis of NVAf at (previous, at or during hospital stay)
Oral anticoagulation (OAC) at = YES
▪ Warfarin derivatives
▪ New OAC (NOAC)
• If NOAC
○ Dabigatran
○ Apixaban
○ Rivaroxaban
Date & time of OAC start: DD/MM/YYYY, time: clock
OAC at discharge = No
1) Date of foreseen start of OAC if not started during hospital stay
Date: DD/MM/YYYY
Aspirin
mRS Score
NIHSS
Systolic Blood Pressure
Diastolic Blood Pressure
Date of
Dipyridamole
Clopidogrel
Other Antiplatelet

Anticoagulants Oral
Dabigatran
Dabigatran Dose
Date of Dabigatran Initiation
Anti Diabetic Oral
Antihypertensive Oral
Statin
Other
Type Of Stroke
Type Of Stroke Ischemic
Type Of Stroke Haemorrhagic
Date Time Of Death
Cause Of Death
At 3-months
Modified Rankin Scale score
If mRS=6=Dead, date/time of death
Cause of death
Patients with NVAf at discharge/ 7d but patient has not been prescribed Warfarin or NOAC (Dabigatran, Apixaban, Rivaroxaban at
1) Has the patient been prescribed Dabigatran after discharge?
If YES questions below will also be shown.
2) Date of initiation of Dabigatran for stroke prevention in NVAf
Date: DD/MM/YYYY
Dose:
Patients with NVAf has been prescribed dabigatran at discharge
Is the patient continuing the prescribed Dabigatran at 3 months follow up since start of the treatment?
- Yes/ No/ Unknown
If No, date of stop of treatment:
Reason for stop of treatment:
- Has the OAC treatment been changed?
If Yes,
Which treatment:

7.2 Appendix 2

CHADS₂ Stroke Risk Score

CHADS ₂ components	Points
Congestive heart failure	1
Hypertension	1
Age 75 years or older	1
Diabetes mellitus	1
Prior cerebral ischemia (i.e., stroke, TIA)	2
Maximum score	6

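### Does the Appendix 1 rule on previous stroke or TIA remove eligible prior-TIA patients from the primary analysis?

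*SAP*

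**What the plan says.** **Eligibility.** Protocol 9.2 and SAP 4.1 give the same criterion, "Patients presenting with their first acute ischemic stroke", and Protocol 9.1 adds "All patients with NVAF will be included that present with the first ever ischemic stroke". The only exclusion (Protocol 9.2, SAP 4.2) concerns participation in an investigational trial. Neither a previous TIA nor a previous haemorrhagic stroke is ruled out.

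**Covariates.** SAP 3.5 lists prior TIA among the variables that characterise patients. The reasons for dose in SAP 3.3 include a history of TIA.

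**Form rule.** Under the hospital-stay heading of SAP 7.1 Appendix 1 stands "Rules: Questions below will be activated if", followed by two conditions: "Previous stroke or TIA = NO" and non-valvular AF present. The items listed next are oral anticoagulation (yes, no, unknown) and, if yes, the drug.

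**Start and dose.** The discharge/day-7 block of the same appendix holds the date and time of anticoagulant start, the dabigatran dose and "Date of Dabigatran Initiation". The 3-month block asks "Has the patient been prescribed Dabigatran after discharge", then date and dose. Protocol 9.4 times the discharge form "At 7 day or discharge if occurred earlier than 7 days" and says that in-hospital data include "any start/stop/change dabigatran treatment".

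**The concern.** The form rule is narrower than eligibility, and neither document comments on the difference or says how far down the appendix the rule extends. Read widely, it would also close the dabigatran fields at discharge and 3 months to anyone with an earlier stroke or TIA. Three things would follow.

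- The primary distribution would describe patients with no previous stroke or TIA, under the label of first ischaemic stroke.
- The missing-value category in SAP 6.1 would not show the loss, because those patients would never be identified as dabigatran-treated.
- Prior TIA would be 0% in every time band, so its standardised difference would be undefined, and the stroke/TIA item would add no variation to CHADS2.

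Even on a narrow reading, a question never shown might be counted as no anticoagulation, both in the channeling comparison (Protocol 9.12) and in the analysis of reasons for not starting (SAP 6.2.2).

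**Working it through.** The plan contains no figure on this point to reproduce, and its target of about 1000 patients is not the result of a calculation. The check is mainly one of text.

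**1. How far does the rule reach?** The order of Appendix 1 is: baseline items (previous stroke and previous TIA as separate fields), time logistics, acute intervention, hospital stay with the rule, 2-hour form, 24-hour form, discharge/day 7, 3 months.
- If the rule ran past its own heading, the 2-hour and 24-hour NIHSS and blood pressure, and the 24-hour imaging, would also be limited to AF patients without earlier stroke or TIA. Protocol 9.4 describes the 24-hour data with no such limit.
- The 3-month block sets its own conditions: AF, and the anticoagulant status at discharge. It restates AF but not TIA. That fits conditions set block by block.
- The prior-TIA covariate and the TIA entry among the dose reasons presuppose that such patients are in the dabigatran set.

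**2. What is lost on the narrow reading?** The gated items shown are anticoagulant status and drug name. Neither is the start date or the dose. Drug, start date and dose can all be taken from the discharge/day-7 block or, for later starts, the 3-month block.

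**3. Starts in hospital after the day-7 form.** These may meet only the 3-month question, which is worded for the period after discharge. But the hospital-stay block shows no date field for any patient, so this limitation does not depend on TIA history and does not come from the rule.

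**4. Not asked versus no.** The gated item has an unknown option, so a blank is distinguishable from a recorded no. The channeling groups rest on treatment within 3 months, for which the later fields are available. The SAP 6.2.2 analysis tabulates responses given, and an unasked patient contributes none.

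**5. Size if the start fields were gated after all.** The share p of eligible starters with an earlier stroke or TIA is not in the documents; p = 5-15% is an assumption. So is a difference d = 10 points between these patients and the rest in their share of a time band.
- Shift in the band = p × d: 0.05 × 10 = 0.5 points; 0.15 × 10 = 1.5 points.
- Sampling half-width for a 20% band, n = 1000: 1.96 × √(0.2 × 0.8 / 1000) = 0.025, or 2.5 points.
- Starters not captured alongside 1000 captured = 1000p/(1 − p): 1000 × 0.05/0.95 = 53; 1000 × 0.15/0.85 = 176.
- Extreme bounds for a band seen at 30%, with none or all of the missing patients in it: 0.30(1 − p) to 0.30(1 − p) + p. This gives 28.5-33.5% at p = 5%, 27.0-37.0% at 10% and 25.5-40.5% at 15%.
- Score ceilings if the index stroke is not scored: CHADS2 6 − 2 = 4; CHA2DS2-VASc 9 − 2 = 7, unless systemic embolism is present. If the index stroke is scored, everyone has the 2 points and prior TIA adds no variation with or without the rule.

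**The case for a change.** The strongest case for a change is that the point decides whom the primary result describes, and that settling it would cost one sentence and one cross-tabulation. If the wide reading were true, the error would be one of selection: a larger sample would not cure it, and the extreme bounds above exceed sampling error. The appendix also leaves the Boolean meaning open. Taken literally, a patient with a TIA but no stroke might satisfy the condition or might not. Some lead-ins in the discharge and 3-month blocks are incomplete in the available text, and the appendix lists selected variables, not the full registry form, so the absence of a TIA condition there cannot be taken as certain.

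What stands is that the mismatch is real and that scope and Boolean meaning are unstated. What does not stand is the step to lost primary data. It needs a rule that passes over two general follow-up forms and overrides the separate lead-in at 3 months, and nothing in either document says so. Nor would the loss stay hidden: previous stroke and previous TIA are recorded at baseline, above the rule, and prior TIA is already due in the descriptive tables. A row of zeros in the dabigatran set would expose a gate at once.

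**Conclusion.** No change to the plan follows. The form rule and the eligibility criteria differ in wording. On the better-supported reading, the rule controls only the in-hospital status and drug items, and patients with a prior TIA who start dabigatran are still identified, dated and dosed from the later forms. Which fields to use, and how to treat an item never shown, are details that an analyst holding the registry extract would settle sensibly without an amendment.

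The number of patients concerned cannot be derived from the documents. Under the less likely reading, and with the assumed 5-15% share and 10-point difference, a time band moves by 0.5-1.5 points, below its half-width of about 2.5 points. The study is descriptive, and SAP section 5 already treats its findings as hypothesis generating. The conclusion rests on the discharge/day-7 and 3-month fields being open to these patients, as the layout indicates. It would need another look only if the extract showed otherwise.
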